### 5.2.4 Visit 4 (Day 15 ± 1)

The following procedures will be performed at Visit 4 (Day 15):

- Review medical history.
- Record medications including start/stop dates, indication, dose and frequency taken after Visit 3.
- Perform and record targeted physical examination as appropriate.
- Assess and record performance status (ECOG).
- Record vital signs (body temperature, systolic / diastolic BP and pulse rate).
- Collect blood samples for blood chemistries, hematology and creatinine clearance.
- Collect urine samples for urinalysis.
- Dispense drug supply for self-dosing.
- Obtain all unused study drug from patient.
- Assess study drug compliance by pill count.
- Assess and record AEs.

### 5.2.5 Visit 5 (Day 22 ± 1 of Cycle 1, first day of Cycle 2)

The following procedures will be performed at Visit 5 (Day 22 of Cycle 1, Day 1 of Cycle 2):

- Review medical history including all cancer treatments received since previous visit.
- Record medications including start/stop dates, indication, dose and frequency taken after Visit 4.
- Perform and record targeted physical examination as appropriate.
- Measure and record weight in kg.
- Assess and record performance status (ECOG).
- Bone marrow aspirate and/or biopsy. Peripheral, Geimsa and Iron stained slides will be collected with each bone marrow aspirate or biopsy. Following Cycles 1 and 2, Day 22 bone marrow aspirates will be collected only every other cycle, i.e., Cycle 4, etc.
- Bone marrow cytogenetics in accordance with local pathology requirements. (Cytogenetics would preferably include at least 20 clones).
- Record vital signs. Measure body temperature, systolic / diastolic BP and pulse rate.
- Collect pre-dose blood samples for pharmacokinetic (PK), pharmacodynamic (PD), and PBMC analyses.
  - These assessments should be collected when the patient reaches steady state. Steady state refers to patients who have received at least 5 days, or 10 consecutive doses, of investigational product. If patients are not at steady state, these assessments will be rescheduled and completed at the next visit in which steady state is achieved.
- Collect blood samples for blood chemistries, hematology and creatinine clearance.
- Collect urine samples for urinalysis.
- Perform urine pregnancy test for female patients who are not postmenopausal or surgically sterile. If urine test is positive, collect blood for a serum pregnancy test. If
serum pregnancy test is positive, withdraw patient from study and contact Medical Monitor.

- Administer BVD-523 and dispense drug supply for self-dosing for Cycle, if appropriate, and remind patient of dosing instructions.
- Collect post-dose blood samples for pharmacokinetic (PK), pharmacodynamic (PD), and PBMC analyses.
  - These assessments should be collected when the patient reaches steady state. Steady state refers to patients who have received at least 5 days, or 10 consecutive doses, of investigational product. If patients are not at steady state, these assessments will be rescheduled and completed at the next visit in which steady state is achieved.
- Assess and record disease status (every 2 cycles).
- Obtain all unused study drug from patient.
- Assess study drug compliance by reviewing pill count.
- Assess and record AEs.

## 5.2.6 Treatment Discontinuation Visit

At the time of study drug discontinuation, the Treatment Discontinuation Visit should be completed for all patients as soon as possible after the last dose of study drug, and every effort should be made to perform the procedures required.

Patients will return to the clinic or will be contacted for a safety follow-up assessment 30 days  $\pm$  3 days after the last dose of study drug was taken; or earlier if subsequent therapy for AML or MDS is initiated prior to 30 days  $\pm$  3 days. Only information about AEs and SAEs will be collected at this visit.

The following procedures will be performed at Treatment Discontinuation Visit:

- Review medical history
- Record medications including start/stop dates, indication, dose and frequency.
- Perform and record physical examination.
- Assess and performance status (ECOG).
- Record vital signs. Measure body temperature, systolic / diastolic BP and pulse rate.
- Perform and record ophthalmology examination.
- Perform urine pregnancy test for female patients who are not postmenopausal or surgically sterile. If urine test is positive, collect blood for a serum pregnancy test.
- Assess and record disease status.
- Bone marrow aspirate and/or biopsy. Peripheral, Geimsa and Iron stained slides will be collected with each bone marrow aspirate or biopsy. Collection not needed if termination is due to progression.
- Bone marrow cytogenetics in accordance with local pathology requirements. (Cytogenetics would preferably include at least 20 clones). Collection not needed if termination is due to progression. Collect blood samples for blood chemistries, hematology and creatinine clearance.

- Collect urine samples for urinalysis.
- Assess and record AEs.
- Obtain all unused study drug from patient.
- Assess study drug compliance by reviewing pill count.

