# 9.3 RECORDING OF ADVERSE EVENTS AND SERIOUS ADVERSE EVENTS

Recording and reporting of adverse events should be in accordance with the FDA "Guidance for Industry and Investigators Safety Reporting Requirements for INDs and BA/BE Studies" of December 2012.

Any AE is to be recorded in the eCRF. In order to avoid vague, ambiguous, or colloquial expressions, the AE should be recorded in standard medical terminology rather than the patient's own words. Whenever possible, the investigator should combine signs and symptoms that constitute a single diagnosis.

The existence of an AE may be concluded from a spontaneous report of the patient; from the physical examination; or from special tests, e.g., ECG, laboratory assessments, or other study-specified tests (source of AE).

The reporting period begins from the time that the patient provides informed consent through and including 30 calendar days after the last administration of BVD-523. AEs may occur in the specified follow-up period. Any SAE occurring after the reporting period must be promptly reported if a causal relationship to the investigational drug is suspected. If the patient begins a new anticancer therapy, the safety reporting period ends at the time the new treatment is started, however, death must always be reported when it occurs during the 30-day reporting period irrespective of intervening treatment.

Each AE is to be evaluated for duration, severity, seriousness, and causal relationship to the investigational drug. The action taken and the outcome must also be recorded. In the event that a rash is noted and reported as an AE, the rash should be documented with photographs as soon as it is reported through resolution. Patients must give consent for photographs to be taken.

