### 10.2 ADVERSE EVENTS

An adverse event is defined as any untoward medical occurrence in a subject administered a medicinal product that does not necessarily have a causal relationship with this treatment. This includes an exacerbation of pre-existing conditions or events, inter-current illnesses, drug interaction, or the significant worsening of the indication under investigation that is not recorded elsewhere in the eCRF under specific efficacy assessments. The reporting period of an AE begins from the time that the subject provides informed consent through and including 30 calendar days after the last administration of BVD-523 (or at the time when a subject begins a new anticancer therapy). Anticipated fluctuations of pre-existing conditions, including the disease under study that does not represent a clinically significant exacerbation or worsening, need not be considered AEs.

The severity of an AE will be graded according to the National Cancer Institute (NCI) Common Terminology Criteria for Adverse Events (CTCAE), version 4.03 with values of Grade 1 to Grade 5 (increased in severity). For AEs not covered by NCI CTCAE, the severity will be characterized as "mild," "moderate," or "severe" according to the following definitions:

- Mild events are usually transient and do not interfere with the subject's daily activities.
- Moderate events introduce a low level of inconvenience or concern to the subject and may interfere with daily activities.
- Severe events interrupt the subject's usual daily activities.

All AE relationship to the study drug, BVD-523, are classified as "unrelated," "possibly related," or "related."

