### **Treatment Emergent Adverse Event**

A treatment emergent adverse event (TEAE) is any AE temporally associated with the use of BVD-523 (from BVD-523 initiation until 30 calendar days after the last administration of BVD-523), whether or not considered related to the study drug. If the onset of an AE is missing and the AE resolution date is either after the initial BVD-523 dose date or missing, then the AE will be considered treatment emergent.

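### The only scheduled safety contact after treatment can come before the 30-day reporting period ends, so late events, and deaths after an early switch of therapy, have no scheduled check.

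*Protocol*

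**What the plan says.** Four passages set the end of safety follow-up.

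- **Contact, Protocol 5.2.6.** "Patients will return to the clinic or will be contacted for a safety follow-up assessment 30 days", plus or minus "3 days after the last dose of study drug was taken". It may also be made "or earlier if subsequent therapy for AML or MDS is initiated prior to 30 days" plus or minus the same 3 days. The visit schedule (Table 6.3) shows no later contact.
- **Reporting period, Protocol 9.3.** AEs are reportable "through and including 30 calendar days after the last administration of BVD-523". If new anticancer therapy begins, "the safety reporting period ends at the time the new treatment is started". Deaths are the exception: "death must always be reported when it occurs during the 30-day reporting period irrespective of intervening treatment".
- **AE period, SAP 10.2.** It has the same 30 days, "or at the time when a subject begins a new anticancer therapy". The exception for deaths is not repeated.
- **Treatment-emergent AE (TEAE) definition, SAP 10.2.** The window runs "from BVD-523 initiation until 30 calendar days after the last administration of BVD-523". It is not shortened when new therapy starts.

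**The concern.** A site can follow Section 5.2.6 exactly, make its one contact on Day 27, and never be prompted to ask about Days 28 to 30. A site that makes the contact when the patient moves to other therapy in the second week is never prompted to find out whether the patient was alive on Day 30, although Section 9.3 requires a death in that interval to be reported.

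Safety and tolerability form a primary objective. Any error from this source runs one way, toward counting too few deaths and serious adverse events (SAEs). With 60 patients, one missed death changes a reported proportion by 1/60, or 1.7 percentage points.

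The SAP adds a separate ambiguity. An AE after an early switch lies outside its AE reporting period but inside its TEAE window.

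**Working it through.** The plan gives no figure for this point, so there is none to reproduce. The check is a day count followed by an illustrative risk.

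**Inputs**
- Contact: Day 30 ± 3, so Day 27 to Day 33, or earlier at new therapy (Protocol 5.2.6).
- AE reporting: to Day 30 inclusive, or to the start of new therapy (Protocol 9.3).
- Death reporting: to Day 30 in all cases (Protocol 9.3).
- Planned patients: 60 (SAP Section 4).
- Median survival: 0.4 years for high-risk and 1.1 years for intermediate-2 MDS (Protocol Section 1).

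**Step 1: no new therapy.** Days without a scheduled contact = max(0, 30 − contact day).

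| Contact day | Uncovered days, AEs and deaths | Share of 30 days |
|---|---|---|
| 27 | 3 | 10% |
| 28 | 2 | 6.7% |
| 29 | 1 | 3.3% |
| 30 to 33 | 0 | 0% |

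**Step 2: new therapy on day d, with the contact made that day (assumed).** The protocol's AE period ends on day d, so the uncovered AE days are 0. For deaths, and for the SAP's TEAE window, the uncovered days are 30 − d.

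| d | AE days (Protocol 9.3) | Death days | SAP TEAE days |
|---|---|---|---|
| 7 | 0 | 23 | 23 |
| 14 | 0 | 16 | 16 |
| 21 | 0 | 9 | 9 |

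**Step 3: illustrative death risk.** With constant hazard, risk over t days = 1 − exp(−ln 2 × t / median). The medians in days are 0.4 × 365.25 = 146.1 and 1.1 × 365.25 = 401.8.

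- t = 3: 1 − exp(−0.6931 × 3 / 146.1) = 1.4%; 1 − exp(−0.6931 × 3 / 401.8) = 0.5%.
- If all 60 patients were contacted on Day 27: 60 × 0.01413 = 0.8 deaths; 60 × 0.00516 = 0.3 deaths.
- t = 16 (switch on Day 14): 7.3% and 2.7% per patient.
- t = 23 (switch on Day 7): 10.3% and 3.9% per patient.

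**Step 4: a less extreme spread.** If contacts fell evenly over Days 27 to 33, the mean uncovered time would be (3 + 2 + 1) / 7 = 6/7 day. The expected deaths in the gap among 60 patients would be about 60 × (6/7) × 0.6931 / 146.1 = 0.24, or 60 × (6/7) × 0.6931 / 401.8 = 0.09.

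**The case against.** The strongest reply is that the visit is only one route by which events reach the database. Section 9.3 makes events to Day 30 reportable whether or not a visit prompts them. Section 9.2 requires fatal progression within the reporting period to be recorded as a Grade 5 event. Section 9.8 requires SAEs to be entered within 24 hours of first knowledge. Section 9.7 has unresolved AEs followed and asks patients and investigators for later events that may be related. A symmetric 3-day window is an ordinary operational choice, and a contact on Day 30 to 33 leaves no gap.

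Most of this stands, and it rules out saying that late events go unascertained. It does not supply an active check. Reporting depends on the site learning of the event, and for new events after discontinuation Section 9.7 asks only about those possibly related to the study. An unrelated death or SAE after the contact is the kind most easily missed.

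A reader might also infer three stronger points that the documents do not support.

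- **That AEs are lost after a switch of therapy.** Section 9.3 itself ends AE reporting there, and the early contact in Section 5.2.6 matches that rule. Under the protocol only deaths remain open.
- **That the SAP discards deaths after a switch.** SAP 10.3 lists and summarises all SAEs and deaths, and the death tables in SAP 14.3.2 state no cut at new therapy. The missing exception in SAP 10.2 needs clarifying, but it does not exclude those deaths.
- **That the primary endpoints are at risk.** Dose-limiting toxicities and the maximum tolerated dose are defined on the first 21 days of treatment. No 30-day mortality endpoint is defined.

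**Conclusion.** The point holds in a limited form. The window in Section 5.2.6 allows the last scheduled contact up to 3 days before the reporting period in Section 9.3 closes. After an early switch it leaves 30 − d days of required death reporting with no scheduled check.

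The effect is small for the 3-day gap: 0.3 to 0.8 deaths at most, and 0.1 to 0.2 if contacts are spread evenly. Both figures assume that every patient is alive at the contact and that no death in the gap is learned of by another route. The early-switch gap matters more per patient, at about 4% to 10% for a switch on Day 7, but the documents give no number of switchers, so no total can be stated.

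The risks are a range under assumption. The medians describe MDS risk groups, not AML and not patients who have just stopped study drug, and the hazard is taken as constant. A reader might assume shorter survival and reach a larger count. A 60-day median, for example, gives 60 × (1 − 0.5^(3/60)) = 2.0 deaths, but no such median appears in the documents.

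This is a cheap improvement to safety ascertainment. It does not undermine the trial's main conclusions.

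**What to change.** **Protocol 5.2.6.** Set the safety contact at Day 30 to Day 33 after the last dose, so that it cannot precede the end of the reporting period. The uncovered days for patients without new therapy then fall from at most 3 to 0. For patients contacted early because new therapy starts, record the start date of that therapy and add a Day 30 vital-status check by phone or chart. The uncovered death days then fall from 30 − d to 0. The start date has to be requested explicitly, because Section 5.2.6 limits this contact to AE and SAE information.

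**SAP.** Reconcile the AE period in 10.2, which ends at new therapy, with the TEAE definition in the same section, which does not. The treatment-emergent definition in 7.2, which ends at termination, withdrawal or completion, should be brought into line at the same time. State that deaths through Day 30 are counted regardless of new therapy, as Protocol 9.3 requires.

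**Cost.** The window change needs a written amendment with Sponsor, IRB/EC and Health Authority approval (Protocol 10.4). Early switchers need one brief extra check. The SAP needs a few sentences. No clinic visit is added.

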#### 3.1.1.2 Secondary Objectives

- To assess clinical response in patients with AML or MDS treated with BVD-523 at the recommended Phase 2 dose (RP2D).
- To determine the progression-free survival (PFS) and duration of response (DOR) of AML or MDS patients treated with BVD-523 achieving CR/CRp.

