## 7.2 DISCONTINUATION OF INDIVIDUAL PATIENTS

Patients are to be withdrawn from the study for any of the following reasons:

- Withdrawal of informed consent
- Disease progression (at the discretion of the PI)
- Unacceptable toxicity
- Changes in the patient's condition which render the patient unacceptable for further treatment in the judgment of the PI
- At least 3 interruptions of BVD-523 intake of > 7 days each, or 8 consecutive days
- Patient becomes pregnant (withdrawal is required)
- Patient is lost to follow-up

Patients will also to be withdrawn at any time if the Investigator concludes that it would be in the patient's best interest for any reason. Protocol violations do not lead to patient withdrawal unless they constitute a significant risk to the patient's safety.

Patients can voluntarily withdraw from the trial for any reason at any time. They are to be considered withdrawn if they state an intention to withdraw, fail to return for visits, became lost to follow up for any reason, or if any of the following occurs:

- Discovery of patient ineligibility
- Significant errors in treatment compliance of at least three interruptions of 7 days each, any treatment interruption of ≥8 consecutive days, or incomplete dosing for greater than 7 days
- Missed / unscheduled / off-schedule / incomplete / incorrect assessments that result in patients being put at risk.

In Part 1 of the study, patients who withdraw at any time due to unrelated AEs preceding the last visit of Cycle 1 (Day 22) will constitute an early discontinuation and must be replaced in order to ensure proper data accrual for dose escalation decisions. A patient who experiences a DLT in Cycle 1 and withdraws before Day 22 either because of the toxicity or otherwise, will nonetheless have that DLT counted in the assessment of potential cohort expansion and/or dose escalation (Table 3.2).

In Part 2 of the study, patients who withdraw at any time preceding the last visit of Cycle 2 (Day 43) will constitute an early discontinuation and will not be replaced and will be evaluated in the Intent to Treat analysis. If patients withdraw due to progressive disease or AEs, replacement of such patients potentially introduces bias into the study. If a patient withdraws for other reasons, replacement of the patient will be decided by the Safety Monitoring Committee.

The investigator must determine the primary reason for a patient's withdrawal from the study and record this information on the eCRF.

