# 9.7 POST STUDY ADVERSE EVENTS AND SERIOUS ADVERSE EVENTS

All unresolved AEs should be followed by the investigator until the events are resolved, the patient is lost to follow-up, or the AE is otherwise explained. At the last scheduled visit, the investigator should instruct each patient to report any subsequent event(s) that the patient, or the patient's personal physician, believes might reasonably be related to participation in this study. Prior to the conclusion of the study at the site the investigator should notify the Safety Associate (see Section 9.8) of any death or AE occurring at any time after a patient has discontinued or terminated study participation that may reasonably be related to this study. After study conclusion the investigator should notify BioMed Valley Discoveries, Inc., or their designee, Clinipace Worldwide (CPWW), of any death or AE they are aware of occurring at any time after a patient has discontinued or terminated study Discoveries, Inc., should also be notified if the investigator should become aware of the development of cancer or of a congenital anomaly in a subsequently conceived offspring of a patient that has participated in this study.

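### Disease assessment ends at the Treatment Discontinuation Visit, so PFS and DOR cannot be observed further in CR/CRp patients who stop BVD-523 without progression

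*Protocol*

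**What the plan says.** Protocol 3.1.1.2 sets the objective: "To determine the progression-free survival (PFS) and duration of response (DOR) of AML or MDS patients treated with BVD-523 achieving CR/CRp". Protocol 10.3.6 and SAP 2.3.2 and 9.2 list PFS and DOR in these patients as secondary endpoints.

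On treatment, disease status is assessed at screening, on Cycle 1 Day 22 and every other 21-day cycle after that (Protocol Table 6.3 footnotes). When drug stops, Protocol 5.2.6 says "the Treatment Discontinuation Visit should be completed for all patients as soon as possible after the last dose of study drug". That visit includes disease status and, unless the patient stops for progression, a marrow and cytogenetics. It is the last column of the schedule in both documents.

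One contact follows, about a month from the final dose (30 ± 3 days), or sooner when new AML/MDS treatment begins before then. Its content is limited: "Only information about AEs and SAEs will be collected at this visit".

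Protocol 7.2 lists unacceptable toxicity, long or repeated dosing interruptions and the investigator's judgment of the patient's condition under "Patients are to be withdrawn from the study for any of the following reasons". It has no separate status for a patient who is off drug but still followed.

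On deaths, Protocol 9.3 says "death must always be reported when it occurs during the 30-day reporting period irrespective of intervening treatment". Beyond that period, Protocol 9.7 asks for "any death or AE occurring at any time after a patient has discontinued or terminated study participation that may reasonably be related to this study".

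**The concern.** PFS and DOR need a date of relapse, progression or death for each CR/CRp patient, or a late date known to be event-free. A patient who relapses on drug supplies one. A patient who stops in remission, for toxicity or interruptions for example, is assessed once at about the stop date, and no later disease assessment is planned. No analysis rule can recover dates that were never collected, so this gap is separate from the SAP's lack of a PFS or DOR definition.

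Two things are at stake. Events are lost from an already small set. Also, patients who stop for toxicity or deterioration are unlikely to be a random subset of responders, so censoring them at stop may be informative.

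**Working it through.** **What is collected for a CR/CRp patient who stops without progression**

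| Time | Disease status | Death |
|---|---|---|
| On drug, after Cycle 1 Day 22 | every 2 × 21 = 42 days | yes |
| Discontinuation visit | yes, with marrow | yes |
| To 30 days after last dose | none planned | all deaths |
| Later | none planned | only if possibly related to the study |

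Unscheduled visits (Protocol 5.2.7) are discretionary and require no disease assessment. The safety contact, at 27 to 33 days, falls inside one 42-day assessment interval.

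**The plan's own figure.** Protocol 10.1.2 gives 88% for at least one response among 20 patients at a 10% rate. 1 − 0.9^20 = 0.878, so it reproduces per group. (For both groups at once, 0.878² = 0.77.) The plan gives no figure for PFS or DOR, and this point does not depend on the 88%.

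**Number of responders.** 40 × 0.10 = 4 in Part 2. The 10% refers to a positive response, whereas PFS and DOR cover CR/CRp only, so CR/CRp patients in Part 2 may be fewer. Part 1 patients could add some, since the PFS/DOR objective is not restricted to the RP2D. Four is used as an illustration.

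**Lost events.** Assume a share s of responders stops before relapse. Ends of response seen, on average, are 4 × (1 − s); the chance of seeing all four is (1 − s)^4.

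- s = 20%: 3.2 seen; all four 0.8^4 = 41%
- s = 40%: 2.4 seen; all four 0.6^4 = 13%
- s = 60%: 1.6 seen; all four 0.4^4 = 3%

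**Possible bias if censored at stop.** Assume exponential times, an on-drug median of 6 months (hazard λ = ln 2 / 6 = 0.1155 per month), a stopping hazard c = λs/(1 − s), and a relapse hazard kλ after stopping. With a = λ + c, the true event-free curve is

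S(t) = e^(−at) + [c/(a − kλ)] × [e^(−kλt) − e^(−at)].

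Check for s = 40%, k = 2: c = 0.0770, a = 0.1925, kλ = 0.2310. At t = 5.21, S = 0.367 − 2.0 × (0.300 − 0.367) = 0.50. The true median is 5.21 months. Censoring at stop estimates 6.0, and 6.0/5.21 = 1.15.

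| k | s = 20% | s = 40% | s = 60% |
|---|---|---|---|
| 1 | 6.0 (0%) | 6.0 (0%) | 6.0 (0%) |
| 2 | 5.64 (6%) | 5.21 (15%) | 4.68 (28%) |
| 3 | 5.43 (10%) | 4.81 (25%) | 4.10 (46%) |

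Entries are true medians in months, with the overstatement by the censored estimate of 6.0 in brackets. If stopping were counted as an event, the estimated median would be 6 × (1 − s) = 4.8, 3.6 or 2.4 months.

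**What the 30-day window recovers.** At a constant hazard with median m months, the share of off-drug events within 30 days is 1 − exp(−(ln 2/m) × 30/30.44). This is 20% for m = 3, 11% for m = 6 and 5.5% for m = 12. These are upper limits, because only deaths in the window are collected, not relapses.

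**The case against.** The strongest reply is that little hangs on these endpoints. They are secondary, Protocol 10.3.6 and SAP 9.2 rule out formal efficacy analysis, and SAP 14.2 plans four response tables with no PFS or DOR output. No dose, sample-size or stopping decision uses them. With four events and a 6-month exponential median, the 95% interval is 2 × 4 × 6/17.53 = 2.7 to 48/2.18 = 22 months (chi-square, 8 df), so the shifts in the table would be invisible. This stands, and it limits the severity.

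A reader might also infer more than the documents support:

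- **That all follow-up, including survival, ends when drug stops.** It does not. The discontinuation visit assesses disease after the last dose, every death is reportable for 30 days even after new therapy begins, and later deaths are requested if possibly study-related. The survival gap is unrelated deaths after Day 30.
- **That the start of new therapy is never known.** Within 30 days the site must know it, because it brings the safety contact forward (5.2.6) and ends the safety reporting period (9.3). SAP 8.3 also counts medications up to 30 days after the last dose as concomitant. The contact itself is not set up to record it, and nothing is planned later.
- **That PFS and DOR describe only time on drug.** Progressions seen on drug are real events, and dosing may continue beyond progression (Protocol Table 3.1 footnote), so time on drug and PFS differ.
- **That both endpoints are biased upward.** The SAP states no event definition or censoring rule. Counting stopping as an event would bias them downward, and an unchanged relapse hazard gives no bias under censoring.

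None of these supplies a relapse date for a responder who stops in remission.

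**Conclusion.** The point holds as a gap in data collection. For CR/CRp patients who stop BVD-523 without progression, PFS and DOR cannot be observed beyond about the stop date, apart from deaths to Day 30 and later deaths thought related to the study.

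The loss of events follows directly from the collection rules. With about four responders, each missing end date is a quarter of the evidence on durability. Overstatement of PFS and DOR is conditional: it needs censoring at stop, which the SAP does not specify, and faster relapse off drug. The range of 0% to 46% rests on an assumed 6-month median, stopping shares of 20% to 60% and hazard ratios of 1 to 3; none of these is in the documents.

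Severity is low to moderate: the endpoints are secondary and descriptive, few CR/CRp patients are expected, and the improvement is cheap.

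**What to change.** 1. **Protocol 5.2.6:** add disease status, start date of any new AML/MDS therapy and vital status to the existing 30-day contact.
2. **Protocol 5.2.6 and 7.2:** separate discontinuing study drug from withdrawing from the study, without changing who stops drug or when. For CR/CRp patients who stop without progression and have not withdrawn consent, record relapse from routine-care results (no study-mandated marrow), new therapy and vital status at regular intervals until relapse or death.
3. **SAP 9.2:** count these relapses and deaths as events, and report how many responders were censored at drug stop and why.

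The cost is a protocol amendment, possibly changed consent wording for patients now classed as withdrawn, a few eCRF fields, and phone or record checks for a handful of responders. No procedures or patients are added. One downside remains: off-drug relapse dates from routine care will be less regularly timed than the on-study marrows, and the report should say so.

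If follow-up is not extended, the protocol and SAP should state that PFS and DOR are observable only through the discontinuation visit.
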